CR = complete response; PR = partial response; SD = stable disease; PD = progressive disease; UE = Unable to evaluate; NA = not applicable; ND = not done.

* Unequivocal PD is defined as overall level of substantial worsening in non-target disease such that even in the presence of SD/PR in target disease, the overall tumor burden has increased sufficiently.

**Unequivocal new lesions may be considered not attributable to differences in scanning technique, change in imaging modality, or findings thought to represent something other than tumor. An example of an equivocal new lesion may be a small size where continued treatment and follow-up evaluation may clarify new disease (Eisenhauer et al, 2009).

Modified irRC-RECIST

irRC-RECIST defined by Nishino et al, 2014 will be used with the following modifications.

Otherwise, these guidelines follow irRC-RECIST defined by Nishino et al, 2014.

- Increased total target lesions to a maximum of 10 (up to a maximum of 5 target lesions per organ).
- Increased total new measurable lesions to a maximum of 10 (up to a maximum of 5 new measurable lesions per organ) at each follow-up time point.
- Target lesions and new measurable lesions must be measurable by CT or MRI only; lesions not measurable by CT or MRI are considered as non-target/new non-measurable.

Table 12-7. Modified irRC-RECIST Definition of Measurable Tumor Response

Measurable Tumor Response (Baseline Target and New, Measurable Lesions)	Measurable Tumor Response Definition
Complete Response (iCR)	Disappearance of all lesions (whether measurable or not and whether baseline or new) and confirmation by a repeat, consecutive assessment no less than 4 weeks (28 days) from the date first documented. Any pathological lymph nodes (whether target or nontarget) must have reduction in short axis to < 10 mm.
Partial Response (iPR)	Decrease in tumor burden ^a ≥ 30% relative to baseline confirmed by a consecutive assessment at least 4 weeks (28 days) after first documentation.

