Progressive Disease (iPD)	
Increase in tumor burden^a ≥ 20% and at least 5 mm absolute increase relative to nadir (minimum recorded tumor burden) confirmed by a repeat, consecutive assessment no less than 4 weeks (28 days) from the date of first documented iPD in the absence of clinical instability.
 
 • Unconfirmed iPD (Initial-iPD) - when measurable (target and new measurable lesions) tumor burden increase ≥ 20% and at least 5 mm absolute increase relative to nadir observed at 1 time point or non-consecutive time points. • Confirmed iPD - when measurable (target and new measurable lesions) tumor burden increase ≥ 20% and at least 5 mm absolute increase relative to nadir observed on 2 consecutive time points at least 4 weeks (28 days) apart in the absence of clinical instability. Date of progression is to be the date of initially reported-iPD prior to confirmed iPD.
Stable Disease (iSD)	Neither sufficient shrinkage to qualify for iCR or iPR nor sufficient increase to qualify for iPD.
Unable to Evaluate (iUE)	Any lesion present at baseline or a new measurable lesion which was not assessed or was unable to be evaluated leading to an inability to determine the status of that particular tumor for that time point. Exception: when iPD is documented based on a partial assessment.
Not Applicable (NA)	No target lesions were identified at baseline.
Not Done (ND)	Radiographic images were not performed at this time point to evaluate the response of measurable lesions.

^a Tumor Burden = sum of diameter of target lesions + sum of new, measurable lesions. Diameters used:

- For nodal disease, shortest axis
- For non-nodal disease, longest diameters

Table 12-8. Time Point Modified irRC-RECIST Overall Response Matrix

Measurable Response	Non-measurable Response		Overall Response
	Non-target lesions (by radiographic imaging or clinical assessment)	New, Non-measurable lesions (by radiographic imaging or clinical assessment)	
Target and New, Measurable lesions (tumor burden) ^a (by CT/MRI)	Non-target lesions (by radiographic imaging or clinical assessment)	New, Non-measurable lesions (by radiographic imaging or clinical assessment)	
Decrease 100% ^e	Absent/NA ^d	Absent	iCR ^b
Decrease 100%	Present/ND/UE	Any	iPR ^b
Decrease 100%	Unequivocal progression	Any	iPR ^b
Decrease ≥ 30%	Absent/Present/NA ^d /ND/UE	Any	iPR ^b
Decrease ≥ 30%	Unequivocal progression	Any	iPR ^b
Decrease < 30% to Increase < 20%	Absent/Present/NA ^d /ND/UE	Any	iSD

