Decrease < 30% to Increase < 20%	Unequivocal progression	Any	iSD
Increase ≥ 20% ^f	Any	Any	iPD ^{b,f}
UE	Any	Any	iUE
ND	Any	Any	iUE
NA ^c	Any	Any	iUE

^a Decreased disease relative to baseline, including new measurable lesions only (≥ 10 mm for non-lymph node lesions, ≥ 15mm in short axis for lymph nodes).

^b iCR, iPR, or iPD should be confirmed by a second, consecutive assessment at least 4 weeks (28 days) apart. Rapid clinical deterioration is an exception for confirming initial PD.

^c No target lesions identified at baseline. When a patient has only non-measurable disease (ie, no target lesions identified at baseline) the response will be unevaluable.

^d No non-target lesions identified at baseline.

^e Disappearance of all non-lymph node lesions and all lymph nodes < 10 mm in short axis would also be iCR even if lymph node measurements prevent 100% tumor burden reduction.

^f In addition to relative increase of > 20%, the tumor burden must also demonstrate an absolute increase of > 5 mm from nadir for iPD. If the tumor burden does not demonstrate > 5 mm increase from nadir but tumor burden is increased > 20% from the nadir, response should be recorded as iSD.

Note: Unequivocal iPD of non-target lesions and/or the appearance of new, non-measurable lesions do not constitute overall iPD.

For subjects who have initial-PD, it is at the discretion of the investigator to continue a subject on study treatment until repeat imaging is obtained a minimum of 4 weeks later. Subjects with a global deterioration of health status requiring discontinuation of treatment without objective evidence of PD at the time are to be classified as “clinically unstable” based on the investigator’s clinical judgement of the subject’s overall clinical condition, including performance status, clinical symptoms, and laboratory data. Clinical instability considers the following criteria based on the investigator’s clinical judgement:

Signs and symptoms indicating PD:

- Decline in ECOG performance status
- Rapid clinical progression of disease
- Progressive tumor at critical anatomical sites (eg, cord compression, clinically active brain metastases, compression of vital organ structures) requiring urgent alternative medical intervention

Amendment 3

Protocol Title: Phase 2 Study of Talimogene Laherparepvec in Combination With Pembrolizumab in Subjects With Unresectable/Metastatic Stage IIIB-IVM1d Melanoma Who Have Progressed on Prior Anti-PD-1 Based Therapy

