partial removal/reduction of any target lesion which contained melanoma on pathology evaluation or pathology results were unknown will not be included. The timepoint responses after initial confirmed iPD will not be used to derive BOR. Confirmation of iCR, iPR, and iPD is required as noted in the individual definitions for iCR, iPR and iPD per modified irRC-RECIST (refer to protocol Appendix 10). For the derivation of iBOR, the overall visit response will be considered iSD if it is an unconfirmed iCR or iPR, and iUE if it is either iSD earlier than 77 days after the date of first dose or an unconfirmed iPD when confirmation of iPD is required (ie, initial iPD without clinical instability). As indicated in [Table 5.1](#), iBOR is defined as the best overall visit response in the following order: iCR, iPR, iSD, iPD, or iUE.

Table 5.1 Matrix of Determining iBOR per Modified irRC-RECIST

Visit Overall Response Sequence	Examples	Best Overall Response	Specifications
*, iCR, iCR, *	iPR, iCR, iCR iCR, iCR, iPD	iCR	A confirmatory iCR must be at least 4 weeks (28 days) later; a subsequent iCR within 28 days will not be valid for confirmation and will be ignored; the iCR will also not be confirmed if there is a subsequent iPR/iSD/iPD at any time prior to the next iCR.
*, iPR, iPR, * *, iPR, iCR/iPR, non-iCR, *	iPR, iPR, iPD iPR, iCR, iPD iCR, iPR, iPD	iPR	Criteria for iBOR=iCR not met. A confirmatory iPR/iCR must be no less than 4 weeks (28 days) later; a subsequent iPR/iCR within 28 days will not be valid for confirmation and will be ignored; the iPR will also not be confirmed if there is a subsequent iSD/iPD at any time prior to the next iPR/iCR.
*, iSD, * *, iCR, non- iPR/iCR, * *, iPR, non-iPR/iCR, *	iCR iPD, iCR iPR iPD, iPR, iSD iSD iPD, iSD, iPD	iSD	Criteria for iBOR=iCR or iPR not met. iSD must be ≥ 77 days from date of first dose; however, this is not required for an unconfirmed iCR/iPR.

*,iPD, iPD, * *, iPDci, *
	
iPD, iPD iPD, iSD, iPD, iPD iPD, iUE, iPD iPDci
	
iPD
	
Criteria for iBOR= iCR, iPR, or iSD not met. A consecutive confirmatory iPD must be no less than 4 weeks (28 days) later unless the initial progression qualified for iPDci.; iPDci = the last available iPD “Nonconfirmed Disease Progression with Clinical Instability” as the reason for ending radiographic follow-up.

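### Table 12-8 footnote f sends a small rise from nadir straight to iSD without checking the change from baseline; taken literally it contradicts Table 12-7 and can cancel the confirmation of a valid iPR.

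*Protocol*

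**What the plan says.** Protocol Appendix 10 (Section 12.10) gives the modified irRC-RECIST rules in two tables.

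- **Table 12-7, iPR:** a fall in tumor burden of at least 30%, "relative to baseline confirmed by a consecutive assessment at least 4 weeks (28 days) after first documentation".
- **Table 12-7, iSD:** "Neither sufficient shrinkage to qualify for iCR or iPR nor sufficient increase to qualify for iPD".
- **Table 12-8, rows for a decrease of 30% or more:** the overall response is iPR.
- **Table 12-8, footnote f** (attached to the row for an increase of 20% or more): "the tumor burden must also demonstrate an absolute increase of > 5 mm from nadir for iPD". If that condition fails but "tumor burden is increased > 20% from the nadir, response should be recorded as iSD".
- **Table 12-8, footnote e:** once all non-nodal lesions are gone, "all lymph nodes < 10 mm in short axis would also be iCR", even where node measurements keep the sum above zero.

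Section 5 of the SAP derives iBOR from investigator visit responses and refers to Appendix 10 for the definitions. Its Table 5.1 adds that "the iPR will also not be confirmed if there is a subsequent iSD/iPD at any time prior to the next iPR/iCR", and an unconfirmed iCR or iPR counts as iSD. iORR is the share of subjects whose iBOR is iCR or iPR.

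**The concern.** The 5 mm condition exists so that a trivial rise from a very small nadir is not called progression. Footnote f does that, but then assigns iSD outright when it should only rule out iPD. A subject with a deep response and a little residual disease can show a rise above 20% from nadir while far below baseline. Such a visit has two prescribed codes in the same appendix.

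The code matters because irRC-RECIST response must be confirmed. One iSD between two iPR visits breaks the pair, and the subject leaves the iORR numerator. The same subject then cannot count towards iDRR and does not enter iDOR, which starts from a response that is later confirmed. These are key secondary endpoints, and the rule bears hardest on responders with small residual disease. The SAP contains nothing that overrides footnote f.

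**Working it through.** **1. The worked conflict.** Baseline 30 mm, week 12 = 10 mm (new nadir), week 24 = 13 mm.

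- From nadir: (13 − 10)/10 = +30%, and +3 mm. The rise is over 20% and not over 5 mm, so footnote f gives iSD.
- From baseline: (30 − 13)/30 = 57% decrease. Table 12-7 and the matching Table 12-8 row give iPR.
- By Table 12-7 the sequence is iPR, iPR and iBOR is iPR. By footnote f it is iPR, iSD and iBOR is iSD.

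**2. When it can happen.** A rise above 20% but not above 5 mm requires 0.20 × nadir < 5 mm, so nadir < 25 mm. The whole zone is still iPR if baseline is at least (nadir + 5)/0.7.

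| Nadir | Zone | Whole zone is iPR if baseline is at least |
|---|---|---|
| 10 mm | above 12, up to 15 mm | 15/0.7 = 21.4 mm |
| 20 mm | above 24, up to 25 mm | 25/0.7 = 35.7 mm |

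At a rise of exactly 5 mm the separate boundary discrepancy applies (see the fix).

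**3. What later scans do** (visits 12 weeks apart).

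| Baseline, then visits (mm) | iBOR with footnote f | iBOR by Table 12-7 |
|---|---|---|
| 40: 10, 14, 14, 14 | iSD | iPR |
| 100: 20, 24.5, 24.5 | iSD | iPR |
| 100: 20, 20, 24.5 | iPR | iPR |
| 100: 20, 24.5, 20, 19 | iPR | iPR |

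A response confirmed before the rise is safe, and a later consecutive pair restores one that was lost. A stable plateau just above the nadir is not restored, because the nadir stays the reference and every later visit is coded iSD again.

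**4. Cost per responder.** Cohort 1: 1/27 = 3.7 points. Cohorts 2, 3 and 4: 1/15 = 6.7 points each. All subjects: 1/72 = 1.4 points. The documents give no figure for iORR. For scale, the exact interval that the sample size sections state for 18/72 (25.0%; 15.5 to 36.6) reproduces. With one responder fewer it is 17/72 = 23.6% (14.4 to 35.1).

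**5. How often, under assumptions.** The documents give no baseline sums, measurement error or response kinetics. Assume constant true burden after week 12, independent error with SD 1 to 2 mm per lesion, 1 to 3 equal target lesions of at least 10 mm at baseline, a baseline sum of 20 to 60 mm and 50% to 70% shrinkage. Among simulated subjects at least 30% below baseline at both week 12 and week 24, count those whose week 24 rise is above 20% and not above 5 mm. Over 126 settings (400,000 subjects each) the share runs from 0% to about 31%.

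| Baseline sum, fraction left, lesions, SD | Constant burden | True burden 10% lower at week 24 |
|---|---|---|
| 20 mm, 0.5, 1, 1.5 mm | about 19% | about 10% |
| 30 mm, 0.4, 1, 1.0 mm | 6.2% | 1.1% |
| 40 mm, 0.4, 2, 1.5 mm | about 12% | 6.0% |
| 60 mm, 0.3, 3, 1.0 mm | 7.1% | 2.0% |

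With a baseline sum of 60 mm and 50% shrinkage the share is close to zero, because the nadir is near 30 mm. With a baseline sum of 100 mm and 3 to 5 lesions it is 0% to 0.3%.

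**The case against.** The best defence is that footnote f hangs only on the row for an increase of 20% or more, while the rows for a decrease of 30% or more give iPR and do not carry it. With the Table 12-7 definition of iSD, a careful investigator could read the footnote as meaning only that the visit is not iPD. That reading is sensible, and the documents do not show which one sites used. But the footnote names a category and sets no baseline condition, so the text does not compel that reading, and about 60 sites were planned.

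Four stronger readings might be inferred and are not supported.

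- **That iORR is understated.** This follows only where footnote f was applied over Table 12-7.
- **That every affected responder is lost at the primary analysis.** The cut comes when all treated subjects have had at least 24 weeks of opportunity. With accrual planned at about one year, the earliest could have had about 24 + 52 = 76 weeks, or six scheduled scans. Only late enrollees have just two, and a later pair of responses restores the others.
- **That complete responses are clearly miscoded.** A residual normal node going from 6 to 8 mm is +33% and +2 mm, hence iSD by footnote f and iCR by footnote e. The two are in tension, but footnote e addresses this case directly and may be read to govern.
- **That the main result is affected.** Modified RECIST v1.1 has no such footnote and its response needs no confirmation. iDCR counts iSD as control. All analyses are descriptive, and no formal comparison of iORR with ORR is planned.

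**Conclusion.** The contradiction is real and stands on the text alone: one visit can be iPR by Table 12-7 and iSD by footnote f, and SAP Table 5.1 carries the difference into iBOR. Where the footnote is followed literally, the error can only lower iORR; it can also lower iDRR and change who enters iDOR. It requires a nadir below 25 mm, a rise before the response is confirmed, and no later consecutive pair of iPR/iCR at least 28 days apart.

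The size is not established. The 0% to about 31% range rests wholly on the stated assumptions, and larger baseline sums or continued shrinkage reduce it. With cohorts of 15 and 27, a single misclassified subject would be visible in a cohort's iORR. This is a secondary-endpoint definition that should be corrected; it does not threaten the primary result.

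**What to change.** Change the last clause of footnote f so that a visit failing the absolute-increase condition is *not iPD; assign iCR, iPR or iSD by comparison with baseline (Table 12-7, footnotes a and e)*. Add a programmed check on the diameters already collected that queries any investigator iSD visit where recorded burden is still at least 30% below baseline. The investigator answers the query, so the endpoint stays investigator-assessed. Deriving visit responses by program would replace that endpoint and is not needed.

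Separately, footnote f uses strict inequalities (above 20%, above 5 mm) where Table 12-7 uses inclusive ones, for example "at least 5 mm absolute increase relative to nadir observed at 1 time point or non-consecutive time points". A rise of exactly 5 mm can thus be iPD in one place and iSD in the other. Treatment decisions follow these criteria, so the sponsor must reconcile the two passages; the rewording above should not settle that boundary by accident.

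Cost: one sentence in Appendix 10, one edit check, and some site queries. No new data are needed.

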Statistical Analysis Plan

[figure not shown]
Protocol Title:	Phase 2 Study of Talimogene Laherparepvec in Combination With Pembrolizumab in Subjects With Unresectable/Metastatic Stage IIIB-IVM1d Melanoma Who Have Progressed on Prior Anti-PD-1 Based Therapy	
Short Protocol Title:	MASTERKEY-115	
Protocol Number:	20180115	
NCT Number:	NCT04068181	
Authors:		
Sponsor:	Amgen Inc. [name]	
SAP Date:	Document Version	Date
	Original (v1.0)	20 March 2020
	Amendment 1 (v2.0)	12 August 2021

[figure not shown]

Version Number	Date (DDMMYYYY)	Summary of Changes, including rationale for changes
Original (v1.0)	20MAR2020	
Amendment 1 (v2.0)	12AUG2021	

 
 • Updated the date for this SAP amendment • Updated the List of Abbreviations • Updated the Introduction • Updated the Section 3.2 Sample size a total of 72 subjects were enrolled in the study (instead of N = 100 subjects planned at the beginning of the study). • Updated the Section 5. Definition Best overall response (iBOR) per modified irRC-RECIST From: ... For the derivation of iBOR, the overall visit response will be considered iSD if it is an unconfirmed iCR or iPR, and iUE if it is either iSD earlier than 84 days after the date of first dose or an unconfirmed iPD when confirmation of iPD is required (ie, initial iPD without clinical instability). ... To: ... For the derivation of iBOR, the overall visit response will be considered iSD if it is an unconfirmed iCR or iPR, and iUE if it is either iSD earlier than 77 days after the date of first dose or an unconfirmed iPD when confirmation of iPD is required (ie, initial iPD without clinical instability). ... And the corresponding Table 5-1. Matrix of Determining iBOR per Modified irRC-RECIST • Updated the Section 5. Definition Best overall response (iBOR) per modified irRC-RECIST • Updated the Section 5. Definition Best overall response (BOR) per modified RECIST 1.1 From:

		
... For the derivation of BOR, the overall visit response will be considered UE if it is SD earlier than 84 days after the date of first dose. ...
 
To:
 
... For the derivation of BOR, the overall visit response will be considered UE if it is SD earlier than 77 days after the date of first dose. ...
 
• Updated the Section 5. Definition Lesion-level 
From:
 
Lesion-level endpoints will be censored on or after the earliest event of the start of the first subsequent anticancer therapy, merger with another lesion, or resection (except if pathology result indicates absence of melanoma). ...
 
To:
 
Lesion-level endpoints will be censored at the earliest event of after the start of the first subsequent anticancer therapy, on or after merger with another lesion, or on or after resection (except if pathology result indicates absence of melanoma). ...
 
• Updated the Section 5. Definition PD-L1 Status 
From:
 
PD-L1 expression from tumor biopsy tissue samples will be reported as positive or negative. PD-L1 expression is said to have positive status if the tumor performance score (TPS) is $\geq 1\%$, and negative status if TPS is $<1\%$.
 
To:
 
PD-L1 expression is said to have positive status if the combined positive score (CPS) is $\geq 1\%$, and negative status if CPS is $<1\%$.
 
• Updated the Section 9.6.1 Adverse Events 
From "A listing of all AEs, EOs for talimogene laherparepvec and pembrolizumab ECI will be provided. Listing of SAEs reported with event onset 90 days after the last dose of study therapy or 30 days after last

--	--	---

		
dose of study therapy if the subject initiates new anticancer therapy, whichever is earlier, will be provided.”
 
To:
 
“A Listing will be provided for treatment-emergent adverse events and treatment-emergent serious adverse events. In addition, death on study will be listed.”

--	--	---

Table of Contents

1.	Introduction.....	9
2.	Objectives, Endpoints and Hypotheses.....	9
2.1	Objectives and Endpoints/Estimands	9
2.2	Hypotheses and/or Estimations.....	11
3.	Study Overview	11
3.1	Study Design.....	11
3.2	Sample Size.....	12
3.3	Adaptive Design.....	12
4.	Covariates and Subgroups	12
4.1	Planned Covariates.....	12
4.2	Subgroups.....	13
5.	Definitions.....	13
6.	Analysis Sets	21
6.1	Full Analysis Set.....	21
6.2	Safety Analysis Set	21

FAS	Full Analysis Set
HSV	herpes simplex virus
iCR	complete response (by modified irRC-RECIST)
iCRR	complete response rate (by modified irRC-RECIST)
iDCR	disease control rate (by modified irRC-RECIST)
iDRR	durable response rate (by modified irRC-RECIST)
iDOR	duration of response (by modified irRC-RECIST)
iORR	objective response rate (by modified irRC-RECIST)
iPD	progressive disease (by modified irRC-RECIST)
iPR	partial response (by modified irRC-RECIST)
iPFS	progression free survival (by modified irRC-RECIST)
irRC-RECIST	immune-related Response Criteria simulating Response Evaluation Criteria in Solid Tumors
iSD	stable disease (by modified irRC-RECIST)
KM	Kaplan-Meier

LDH	lactate dehydrogenase
NCT	National Clinical Trials
ND	Not done
ORR	objective response rate (by modified RECIST 1.1)
OS	overall survival (by modified RECIST 1.1)
PD	Progressive disease (by modified RECIST 1.1)
PD-1	programmed cell death-1
PD-L1	programmed cell death-1 ligand 1
PFS	progression free survival (by modified RECIST 1.1)
PR	partial response (by modified RECIST 1.1)
qPCR	real-time polymerase chain reaction
RECIST	Response Evaluation Criteria in Solid Tumor
SAS	Safety Analysis Set
SD	Stable disease (by modified RECIST 1.1)
TEAE	Treatment Emergent Adverse Event
UE	Unevaluable
ULN	upper limit of normal
	

1. Introduction

[figure not shown]
The purpose of this Statistical Analysis Plan (SAP) is to provide details of the statistical analyses that have been outlined within the protocol for study 20180115, Talimogene Laherparepvec (T-VEC), Amendment 3 dated **09 June 2021**. The scope of this plan includes the futility analysis, the primary analysis and the final analysis that are planned and will be executed by the Amgen Global Biostatistical Science department unless otherwise specified.

2. Objectives, Endpoints and Hypotheses

